**Evaluation of Wear Experience with PRECISION7® For Astigmatism Contact
Lenses in Neophyte Lens Wearers**

NCT: NCT06751225

Document Date: 25-Nov-2024

Evaluation of Wear Experience with PRECISION7® For Astigmatism Contact Lenses in Neophyte Lens Wearers

[name], OD MS

The Ohio State University College of Optometry
Innovation in Vision and Eye care Research Group - iVERG
[name]
[name]
[contact]

Purpose

The purpose of this study is to explore the wear experience with PRECISION7® For Astigmatism lenses in adults who have not previously worn contact lenses.

Study Overview

This open-label study is of adults with astigmatism who have never worn contact lenses. Subjects will be fit into PRECISION7® For Astigmatism contact lenses and will wear lenses for approximately 3 weeks. Subjects will return for vision and lens fit assessments and will complete surveys about their wear experience.

Background

Soft daily wear contact lenses are used by an estimated 40.9 million adults in the United States.¹ Contact lenses which are worn for daily wear are considered minimal risk by the FDA, and risks to wearers are minimized by proper lens care and hygiene. The subjects in this study are adults with astigmatism that have never worn contact lenses who will be fit into PRECISION7® For Astigmatism, a 1-week replacement reusable contact lens.

Key Endpoints:

- Subjective assessment of P7 experience with CLDEQ-8, Visual Analog Scale survey of lens wear symptoms, and questionnaire about quality of life/preference of lens modality experiences.

Study Time Points:

After responding to recruitment material, potential participants will respond to pre-screening questions to determine initial eligibility. Those eligible will be scheduled for a screening visit and will complete the informed consent process. Manifest refraction, Best Corrected Visual acuity, and an evaluation of the participant's ocular health will occur. The OSDI questionnaire will also be complete to assess if the participant has dry eye. The fit of PRECISION7® For Astigmatism lenses will be analyzed and optimized before dispensing a pair of lenses for 1 week of wear (-3 days). The participant will be trained on insertion/removal and contact lens hygiene.

Visit 2: PRECISION7® For Astigmatism follow up visit. Vision, lens fit and ocular health will be assessed. If lens fit and eye health are acceptable, PRECISION7® for Astigmatism Contact Lenses will be dispensed and a contact lens follow-up visit scheduled for 2 weeks (-3 days). If an additional study visit is required because the lens power or fit must be changed at this visit, new lenses will be dispensed/ordered and Visit 2 will be repeated after 1 week of wear with the optimized lenses. (Participants will be compensated for a repeat visit.)

Visit 3: The contact lens follow up visit will occur approximately 2 weeks (-3 days) following the initial fitting. Subjects will have visual acuity, an assessment of ocular health, and lens fit completed. Subjects will then complete surveys about their lens wear experience.

All surveys at visit 3 will be completed in REDCap.^{2,3}

Surveys will include:

CLDEQ-8

VAS survey of comfort/dryness/vision

0-100 scale:

Overall vision throughout the week

Overall vision while on digital device

Stability of vision at end of day

Stability of vision throughout the week

Overall comfort throughout the week

Overall comfort throughout the day

Overall comfort while on digital device

End of Study Wear Experience

Convenience of 1 week replacement lens

Would you purchase PRECISION7 for Astigmatism?

How easy is it to apply the lenses to your eye?

How easy is it to remove lenses?

Recruitment

Potential participants may see posters placed on bulletin boards locally, at The Ohio State University, or local eye care offices, student dorms, emails to students, faculty and staff at OSU, online or paper ads, or signs on the OSU buses. Facebook advertising through the CCTS will occur. A search of the electronic medical records of The Ohio State College of Optometry may be done to identify possible subjects who then may be contacted by email or phone with information about the study. Word of mouth referrals by study team members to OSU employees and friends may occur. Emails to alumni of the OSU College of Optometry may be sent for local doctors to notify eligible potential subjects about the study.

Inclusion:

1. Subjects must be new to contact lenses and have astigmatism of -0.75 or greater (within the parameters available for the P7fA lenses)
2. Subjects must have 20/20 or better best corrected visual acuity.

3. Good general health (defined by medication use that has not changed within the last month and the absence of medical conditions or treatments that are deemed confounding to the data as determined by the PI)
4. Ability to give informed consent
5. Willing to spend time for the study. Subjects will be required to attend three study visits and wear contact lenses on days between study visits.
6. Willing and able to wear contact lenses for at least 8 hours per day for 5 days per week during the study as daily wear.
7. Currently not using eye lubricating drops and willing to not use during study.
8. Either gender and 18-40 years of age.
9. Any racial or ethnic origin

Exclusion Criteria:

1. Any active ocular inflammation or infection.
2. Has a systemic condition that in the opinion of the investigator may affect a study outcome variable.
3. Are presbyopic and require or habitually uses reading glasses for near work
4. Is using any systemic or topical medications that in the opinion of the investigator may affect a study outcome variable
5. History of refractive surgery
6. Meets the diagnosis of dry eye disease with OSDI screening score ≥ 13 .
7. Known history of allergy or sensitivity to contact lens solutions and/or sodium fluorescein
8. Is pregnant or lactating or planning a pregnancy during enrollment in the study
9. Is participating in another clinical research study that includes invasive ocular tests
10. An inability to perform contact lens application and removal after instruction.

Consent and Confidentiality

A team member trained in the consent process will provide the consent document for the potential subject to read and will review the procedures with reference to the consent form. The individual is then provided with time to read the consent form and offered the opportunity to ask questions. The participant is explicitly told that they may stop participation at any time. All subjects will have the capacity to give informed consent. If there is any doubt as to the subject's ability to consent to the study, the subject will be excluded from the study. If the subject agrees to take part in the screening or measurement, he or she will sign and date the most recent IRB-stamped consent as will the team member. The subject will be provided with a copy of the consent form.

The investigator team is trained in privacy issues and will be reminded of the importance of patient privacy prior to study initiation. Potential study participants will contact us after seeing advertisements, emails or hearing about the study by word of mouth, giving them the choice of whether or not they wish to participate in a study for people with dry eyes. Privacy is protected by limiting information related to study recruitment only, and no other personal or medical information that should be private to the patients. The PHI needed is only for the purposes of this study. It is highly unlikely, indeed extremely remote that the dry eye symptoms or signs are related to private or personal information that should or would be preferred to be kept confidential to the patients. Risk factors for dry eye rarely relate to matters or conditions that would be personal to the patient such as personal relationships, behaviors or diseases that one prefers to keep private and confidential.

Statistical Analysis

This pilot study is investigating the wear experience of individuals who have not previously worn contact lenses. Sixty potential participants will be screened in order to complete 40 participants. This monadic study will report outcomes with descriptive statistics, and as such, no power calculation is necessary. This size of this study will enroll enough subjects to have robust responses to preference surveys.

Data Management and Security

During the active stages of the study (recruitment to last measurement visit), all paperwork (consents, questionnaires and data forms) for each subject will reside in a subject folder for easy access throughout the study. The folders will reside in the limited-access research area, in a locked file drawer or cupboard. At the completion of the study or disenrollment of a subject the paperwork in the subject's folders will be reorganized into a regulatory binder (consents, W-9s) and a data binder (questionnaire and data forms) and will reside in locked cabinet in the limited-access research area. When the data analysis is completed and the study is considered complete, the binders will be stored in the secure Department or Office Clinical Research Area. Paperwork (questionnaire and data forms) for individuals who participate in the baseline visit but are not eligible to continue the study will be stored in the study regulatory binder in a locked cabinet in the limited-access research area. An electronic file of potential subjects and a file of enrolled subjects with their contact information, as well as electronic files of collected data with the subject number, will reside on a limited-access shared drive with firewall and password protection and is restricted to individuals in the research team. Any electronic data files that contain PHI will be destroyed at the conclusion of the study.

Risks to Subjects and Mitigation

Visit procedures present no greater risk than would be experienced during a routine eye exam or routine contact lens fitting. Learning to apply and remove contact lenses may cause temporary redness or irritation of the eyes. Transient (less than one minute) blurring of vision, or transient (less than one minute) mild stinging may occur when inserting contact lenses. Although rare, contact lens wear is associated eye infection, abrasion, and discomfort, which can all be minimized with proper hygiene and contact lens care, which will be taught to study participants.

Adverse Events

All adverse events will be documented and reported under the guidelines of The Ohio State University Event Reporting guidelines, with any serious, unanticipated and related events being reported to the IRB, by the PI, within 10 days. Adverse Events information will be summarized in the annual report to the IRB. Adverse events will be assessed and determined by [name].

Subject Dismissal

Subjects who, after study team member coaching, are not able to provide analyzable data may be dismissed from the study. Analyzable data is, for example, that which is obtained for the entire measurement interval and provides a readable eye image. Data may not be analyzable if patient isn't able to stand or move freely to utilize the equipment, to name just two causes issues. These issues are usually revealed at the screening assessment visit. Subjects who cannot provide analyzable data will be dismissed for the study. Subjects who do not keep scheduled visits within the required time frame will be dismissed from the study. Study team members will make reasonable efforts to accommodate subjects' schedules.

Protocol Violations, Discontinuation

In the event that a member of the study team or a representative of sponsor becomes aware of a major protocol violation, the IRB shall be notified within 10 working days.

References

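### The timing of Visit 3, the only visit that lists the key-endpoint surveys, is internally inconsistent: its own text counts 2 weeks from the initial fitting, whereas the rest of the schedule implies about 3 weeks of wear.

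*Combined protocol and SAP*

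**What the plan says.** Four statements in the combined protocol and SAP bear on when Visit 3 takes place.

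- Study Overview: subjects "will wear lenses for approximately 3 weeks".
- Study Time Points, fitting visit: the lens fit "will be analyzed and optimized before dispensing a pair of lenses for 1 week of wear (-3 days".
- Visit 2, when fit and eye health are acceptable: lenses are dispensed and "a contact lens follow-up visit scheduled for 2 weeks (-3 days". This sentence names no starting point for the 2 weeks.
- Visit 3: "The contact lens follow up visit will occur approximately 2 weeks (-3 days) following the initial fitting". This is the only statement that names its starting point.

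If the lens power or fit has to change at Visit 2, "new lenses will be dispensed/ordered and Visit 2 will be repeated after 1 week of wear with the optimized lenses".

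At Visit 3, after the clinical assessments, "Subjects will then complete surveys about their lens wear experience". The CLDEQ-8, the VAS items and the end-of-study questions are listed there and at no other visit. The OSDI at screening is an eligibility test. Under Subject Dismissal, a subject who does not keep visits within their time frame is to be dismissed.

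**The concern.** The Visit 3 sentence and the Visit 2 sentence give the same interval, but they cannot share a starting point if the study is to last 3 weeks. Visit 2 is described as a follow-up visit, and the lens is fitted and dispensed at the visit before it, so the initial fitting cannot naturally mean Visit 2.

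Three things are at stake.

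- The meaning of the results. The study is single-arm and descriptive, so the length of wear behind the surveys is part of what each reported figure describes.
- The refit branch. A repeated Visit 2 uses up the time that the Visit 3 sentence allows.
- Who counts as being in window. The dismissal rule depends on it, and the target is only 40 completers.

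One survey item is also sensitive to the interval: "Convenience of 1 week replacement lens". If a fresh pair is started at Visit 2, the number of days from there to Visit 3 decides whether the subject has replaced a weekly lens at home before rating it.

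**Working it through.** All days are elapsed days, with the fitting visit as day 0.

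**Inputs**
- Fitting to Visit 2: 1 week (-3 days), so 7 - 3 = 4 to 7 days (fitting paragraph).
- Follow-up interval in the Visit 2 paragraph: 2 weeks (-3 days), so 14 - 3 = 11 to 14 days.
- Interval in the Visit 3 paragraph: also 11 to 14 days, counted from the initial fitting.
- Total wear in the Study Overview: about 3 weeks, 21 days.

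**Step 1. Reproduce the 3 weeks.** Count the Visit 2 interval from Visit 2. The earliest day is 4 + 11 = 15, the latest is 7 + 14 = 21, and the nominal day is 7 + 14 = 21. This agrees with the Study Overview.

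**Step 2. Apply the Visit 3 sentence.** Visit 3 falls on day 11-14, nominally day 14, or 2 weeks. This does not agree with the Study Overview. Starting the Visit 2 interval at the fitting gives the same 2 weeks.

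**Step 3. Compare.**

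| | Counted from Visit 2 | Counted from initial fitting |
|---|---|---|
| Visit 3, range | day 15-21 | day 11-14 |
| Visit 3, nominal | day 21 | day 14 |
| Visit 2 to Visit 3, range | 11-14 days | 11 - 7 = 4 to 14 - 4 = 10 days |
| Visit 2 to Visit 3, nominal | 14 days | 14 - 7 = 7 days |

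The nominal difference is 21 - 14 = 7 days, and 7/21 is one third of the planned wear. At the bounds it is 15 - 11 = 4 and 21 - 14 = 7 days.

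**Step 4. Refitted subjects.** Assume that new lenses are dispensed on the day and the repeat visit is exactly 7 days later. The repeat Visit 2 is then on day 4 + 7 = 11 to 7 + 7 = 14, the same days as Visit 3 under its own sentence. If the -3 day window also applies to the repeat, it falls on day 4 + 4 = 8 to 14. Even from day 8, a Visit 3 no later than day 14 leaves 14 - 8 = 6 days, short of the 11 that the follow-up needs. Counted from the repeat Visit 2, Visit 3 falls on day 11 + 11 = 22 to 14 + 14 = 28, or from day 8 + 11 = 19 if the wider window applies. Lenses that must be ordered push it later.

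**Step 5. The dismissal rule.** A subject seen on day 21, as the Study Overview implies, is 21 - 14 = 7 days past the end of the window in the Visit 3 sentence.

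**Step 6. The replacement item.** If a fresh pair is started at Visit 2, 11-14 days takes every subject past one weekly replacement at home. At a nominal 7 days the pair is only just due.

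**The case against.** The strongest reply is that the plan is inconsistent but does not fix Visit 3 at the early date. The visit is booked at Visit 2, and staff who count from that day arrive at the 3 weeks in the Study Overview. On that view one phrase is mis-worded and nobody need be surveyed early. This stands as far as it goes. The documents do not show that staff would follow the Visit 3 sentence, and the Visit 2 starting point is itself an inference, though the only one that gives 3 weeks.

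The gap between the two windows is also only one day, from day 14 to day 15, and both the Visit 3 sentence and the Study Overview are approximate. That is fair, so the nominal 7 days is the better measure. The stated tolerance runs only in the early direction, so it cannot carry day 14 towards day 21.

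The exact clash in the refit branch depends on same-day dispensing and a 7-day repeat, and the number of refits is unknown. The first part is right, but Step 4 shows that the follow-up does not fit under the wider window either.

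Finally, a subject surveyed on day 14 has already worn one pair and started a second, and the VAS items ask about the day and the week, which either interval covers. This stands: such a subject can still rate a weekly lens. What may be missing is a replacement made at home.

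**Conclusion.** The inconsistency is real, and the Visit 3 phrase is the part that is wrong, probably through a drafting slip. It is more than a clerical matter because it is the timing rule for the only visit that lists the key-endpoint surveys, it conflicts with the refit branch, and it affects who is in window. Its size, if the phrase is followed, is a nominal 2 weeks of wear instead of 3, and 7 days instead of 14 between Visit 2 and Visit 3. The conclusion rests on counting the Visit 2 interval from Visit 2.

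A reader might infer more than the documents support:

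- That the surveys will be a week early for every subject. This holds only if staff follow the Visit 3 sentence over the Visit 2 scheduling instruction.
- That the sponsor chose a shorter exposure. The 3 weeks in the Study Overview point the other way.
- That ratings would differ. Nothing in the documents shows a difference between 2 and 3 weeks.
- That the loss can be stated in hours of wear. The criterion that subjects be willing and able to "wear contact lenses for at least 8 hours per day for 5 days per week during the study as daily wear" is an eligibility minimum and not a record of wear, so hours would only restate the day counts.

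The study has no power calculation, so no sample size or power figure changes.

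**What to change.** In the Visit 3 paragraph, replace the reference to the initial fitting with: *after the Visit 2 at which lens fit and eye health are accepted*. The 2 weeks (-3 days) stay as they are.

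This restores agreement with the Study Overview, gives a refitted subject a full follow-up interval, and places a Visit 3 delayed by a repeat Visit 2 inside its time frame for the dismissal rule.

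The cost is one phrase. No visit, assessment or subject is added. Refitted subjects stay in the study about a week longer than the others, which the Visit 2 paragraph already implies. Reporting the number refitted and the days in the final lens at Visit 3 (median and range) would be a useful extra, but it is optional and not needed to correct the error.

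### Study team members may recruit friends and university employees into an open-label, single-arm study whose key endpoints are all self-reports, and nothing excludes, records or separates participants with a tie to the team

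*Combined protocol and SAP*

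**What the plan says.** The Recruitment section lists many routes, including "emails to students, faculty and staff at OSU". It then adds: "Word of mouth referrals by study team members to OSU employees and friends may occur". The section on consent and confidentiality also names word of mouth as a way in which participants may hear of the study.

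The nine inclusion and ten exclusion criteria deal with refraction, ocular and general health, medication, age, willingness and handling ability. None mentions study staff, relatives, friends, employees or people who report to the team.

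The Study Overview says: "This open-label study is of adults with astigmatism who have never worn contact lenses". Key Endpoints has a single entry: "Subjective assessment of P7 experience with CLDEQ-8, Visual Analog Scale survey of lens wear symptoms, and questionnaire about quality of life/preference". Vision, fit and ocular health are assessed at visits but are not key endpoints. At Visit 3, once the clinical assessments are done, "Subjects will then complete surveys about their lens wear experience". These surveys are entered in REDCap. The end-of-study items include "Would you purchase PRECISION7 for Astigmatism", with the product named, as well as convenience and ease of application and removal.

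Statistical Analysis describes a monadic pilot reported descriptively, with 60 screened to obtain 40 completers. Data Management and Security restricts the electronic files, which carry the subject number, to the research team.

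**The concern.** In this study the participant is the assessor of every key endpoint and knows which product is being rated. A participant who is a friend of a team member, or who works under one, has a possible reason to answer kindly that a stranger recruited from a bus sign does not. The plan permits that kind of recruitment in so many words, so this is a stated rule and not merely a detail left out.

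With no second arm, a favourable shift has nothing to cancel against. The plan also provides no record of recruitment source or relationship to the team, and no analysis that sets such participants apart. As written, a reader of the results could neither detect the shift nor take it out. The survey responses are the study's main product, and Statistical Analysis relies on the sample size to make the preference answers dependable. A larger sample recruited the same way would not reduce a bias of this kind.

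**Working it through.** **The plan's own figure.** The only sample-size figures are 60 screened and 40 completing. They come without a power calculation, SD, effect size or dropout rate, so there is nothing to reproduce. The 40 is used below only as a denominator.

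**Text check.**
- Is the route permitted? Yes, under Recruitment.
- Is it closed elsewhere? No. The two exclusions that turn on whether something may affect an outcome variable are limited to systemic conditions and medications.
- Is there an objective key endpoint? No; Key Endpoints lists only subjective instruments.
- Is there a comparator? No.
- Is survey completion private from examining staff? The plan does not say. It states REDCap entry and research-team access to the electronic files, and nothing on who is present or who views individual answers.

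**Illustration of size.** If a share f of completers has a tie and rates b points higher than the rest, the overall mean shifts by f × b. The documents give neither f nor b; both are assumptions.
- Low case: 4 of 40 tied, 10 points higher: 4/40 × 10 = 1.0 point on the 0-100 scale.
- High case: 10 of 40 tied, 15 points higher: 10/40 × 15 = 3.75 points.
- Purchase intent, assuming a yes/no answer: 8 of 40 tied and 95% of them say yes, against 60% of the other 32: (8 × 0.95 + 32 × 0.60)/40 = (7.6 + 19.2)/40 = 26.8/40 = 67%, against 60%.

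**Wider assumptions.**
- A share of 5% to 50% and an excess of 5 to 20 points give 0.05 × 5 = 0.25 to 0.50 × 20 = 10 points.
- For purchase intent, 60% in the others against 80% to 95% in those with a tie gives 0.05 × 20 = 1 to 0.50 × 35 = 17.5 percentage points.

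**For scale.** The 95% half-width for a proportion of 60% with n = 40 is 1.96 × √(0.6 × 0.4/40) = 0.152, about 15 percentage points. The 7-point example is less than half of that. But it acts in one direction, and the interval does not reflect it.

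**The case against.** The case on the other side has several parts.

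- **Route.** Word of mouth is permitted, not required, and is one of many routes. Employees of a whole university need not know the team, and friends could mean friends of employees. This stands: the number of tied participants cannot be predicted and may be zero.
- **Motive.** Nothing shows that a friend or employee would think the team wants a favourable rating, and any open-label single-arm survey carries some courtesy bias from everyone. This also stands as a limit on size. It does not explain why a route that could add to the bias should be kept when others are available.
- **Endpoints.** A reader might infer that every key endpoint is an opinion of the product. That goes too far. CLDEQ-8 and the 0-100 items ask about symptoms, comfort and vision, and two end-of-study items ask about handling. These are self-reports, but probably less exposed than purchase and convenience.
- **Privacy.** A reader might infer that answers are open to the person who made the referral, because paperwork including questionnaires "will reside in a subject folder for easy access throughout the study". The documents do not support this. That sentence concerns paper records, held in a locked drawer or cupboard in a limited-access area, whereas the Visit 3 surveys are in REDCap. Team access to the electronic files is stated; that a referring or examining person sees individual answers is not.
- **Purpose.** This is an exploratory pilot with no hypothesis or threshold, so no formal decision would be reversed. That is correct, and it limits the weight of the point.

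**Conclusion.** The point holds as an avoidable risk of bias of unknown size. It is not an arithmetic error or a contradiction. The plan expressly lets team members refer friends and employees, excludes nobody with a tie, and reports open-label self-assessments with no comparator. Any courtesy shift therefore enters the results undiluted, most plausibly in the purchase and convenience items.

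The figures of about 1 to 4 points, or 60% to 67%, rest wholly on assumed shares and excess ratings, and the purchase figure also on an assumed yes/no format, since the plan gives no response scale for that item. They show what would follow, not what will happen.

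A reader might also infer that all staff and students of the optometry college must be barred. The documents do not call for that: a university or college affiliation is not itself a personal or reporting tie, and recording it is enough.

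**What to change.** 1. **Recruitment:** remove friends of study team members from the word-of-mouth route.
2. **Exclusion criteria:** add one line covering study team members, their relatives and close contacts, and people who report to them.
3. **Case record:** note each participant's recruitment source and any other tie to the team or the optometry college.
4. **Statistical Analysis:** report the survey results with and without participants who have such a recorded tie.
5. **Visit 3:** have the surveys completed in REDCap without examining staff present or viewing the responses, and tell participants so.

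The cost is a slightly smaller recruitment pool and one extra descriptive table. The pool matters somewhat, because eligibility is already limited to adults aged 18 to 40 with astigmatism who have never worn lenses and do not meet the dry-eye criterion. The posters, advertisements, bus signs, general emails, records search and local practices already listed remain available. Planned visits, study procedures and sample size stay as they are.

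### Experience surveys are taken only at Visit 3, so anyone given lenses who stops earlier contributes no rating and the results may look more favourable than first-time wear really is

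*Combined protocol and SAP*

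**What the plan says.** Key Endpoints names only self-reported outcomes: "Subjective assessment of P7 experience with CLDEQ-8, Visual Analog Scale survey of lens wear symptoms, and questionnaire about quality of life/preference of lens modality experiences".

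The visit schedule under Study Time Points places these instruments at the last visit. Under Visit 3, after the clinical checks, "Subjects will then complete surveys about their lens wear experience", and "All surveys at visit 3 will be completed in REDCap". The list that follows gives the CLDEQ-8, the 0-100 VAS items and the end-of-study items, including whether the subject would buy the lens. For Visit 2 the text lists clinical checks only: "Vision, lens fit and ocular health will be assessed". Lenses for the remaining period are dispensed "If lens fit and eye health are acceptable"; a power or fit problem leads to new lenses and a repeat of Visit 2.

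Statistical Analysis states "Sixty potential participants will be screened in order to complete 40 participants", then "This monadic study will report outcomes with descriptive statistics, and as such, no power calculation is necessary" and "This size of this study will enroll enough subjects to have robust responses to preference surveys".

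There are several ways to leave before Visit 3. Consent and Confidentiality lets subjects stop whenever they wish. Subject Dismissal removes those who miss visit windows or cannot give analyzable data. Neither section, nor any other, describes an exit survey, a record of the reason for stopping, an analysis set, a missing-data rule, or a report of how many were dispensed lenses against how many completed.

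**The concern.** The stated purpose is to explore the wear experience of adults new to contact lenses. For such people, giving up because of discomfort or poor vision is part of the experience, and Risks to Subjects and Mitigation itself lists irritation and discomfort as possible. Followed as written, the plan asks for ratings and purchase intent only from those who lasted to Visit 3.

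The study has one arm, so there is no comparator in which such selection might partly cancel. Descriptive reporting removes the need for a power calculation, but a percentage still has a denominator. If the result is read as applying to everyone fitted, the completer denominator is the wrong one. Ratings that were not collected when a person left cannot be reliably recovered afterwards.

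**Working it through.** **The plan's own figures.** 40/60 = 66.7%, so the plan allows for a combined loss of 33.3%, and 40/(1 − 1/3) = 60. This loss is back-calculated from the same two numbers, so it is not an independent check. No dropout rate, screen-failure rate, SD or precision target is given.

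**How much of the margin could be stoppers.** The 20 people between 60 and 40 include screen failures. If s of the 60 fail screening and 40 complete, the number dispensed who then stop is k = 20 − s. Thus k = 8 requires s = 12, and k = 10 requires s = 10. The documents do not split the margin, so k is unknown and may be zero.

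**Assumptions for illustration (none is in the documents).** Of 40 completers, 32 would purchase (80%). There are k lens-related stoppers among 40 + k dispensed. Stoppers would have scored 20 to 40 points worse on a 0-100 VAS item.

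**Formulas.**
- Purchase intent over all dispensed, stoppers counted as a no: 32/(40 + k).
- The opposite extreme, stoppers counted as a yes: (32 + k)/(40 + k).
- Completer-only bias in a VAS mean: k/(40 + k) × (completer mean − stopper mean).

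| k | Dispensed | All stoppers no | All stoppers yes | VAS bias, 20-point gap | VAS bias, 40-point gap |
|---|---|---|---|---|---|
| 0 | 40 | 32/40 = 80.0% | 80.0% | 0 | 0 |
| 2 | 42 | 32/42 = 76.2% | 34/42 = 81.0% | 0.95 | 1.9 |
| 4 | 44 | 32/44 = 72.7% | 36/44 = 81.8% | 1.8 | 3.6 |
| 8 | 48 | 32/48 = 66.7% | 40/48 = 83.3% | 3.3 | 6.7 |
| 10 | 50 | 32/50 = 64.0% | 42/50 = 84.0% | 4.0 | 8.0 |

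**Scale.** With an assumed SD of 20, the 95% half-width for a VAS mean at n = 40 (t, 39 df) is 6.4 points. Four stoppers move the mean by well under that. Eight move it by about half of it at the smaller gap (3.3/6.4) and by about the whole of it at the larger (6.7/6.4).

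**The case against.** The strongest reply is that this is a small, open-label, single-arm pilot meant to explore. It has no hypothesis test and makes no stated claim about everyone dispensed lenses. The plan is silent on disposition; it does not say that stoppers will be hidden, and adverse events are documented whether or not a subject completes. All of this is true, and it lowers the severity. It does not supply the missing ratings: adverse-event records do not hold CLDEQ-8, VAS or purchase answers.

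Three stronger readings are tempting and are not supported.

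- A reader might infer that enrolment continues until 40 people finish, with each stopper replaced by someone who tolerates the lens. The text gives a planned number screened and a target number of completers. It states no replacement rule and no open-ended enrolment.
- A reader might infer that every rating is biased upward. Bias needs people who stop after dispensing and who would have rated differently. Neither quantity is given. Someone dismissed for missing a visit window need not differ from the rest. The documents also do not state the scoring direction of the CLDEQ-8, so the safe description is a more favourable picture, not a higher score.
- A reader might take all 20 non-completers as possible lens failures. That would require no screen failures at all, although refraction, acuity, ocular health and the OSDI are assessed at screening.

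Poor fit is also a smaller route out than it first appears. Fit is optimised before dispensing, and a fit or power problem at Visit 2 leads first to a refit and a repeated visit. Only those whose problem is not resolved, or who choose to stop, are lost. People who cannot handle lenses after instruction fall under an exclusion criterion, so their absence is partly a matter of target population.

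Finally, counting stoppers as a no is an imputation, not an observed answer. This is why it belongs in a sensitivity figure and not in the headline.

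**Conclusion.** The point holds as a gap in data collection and in the denominator. As written, the plan obtains no key-endpoint rating from anyone dispensed lenses who stops before Visit 3, and its results describe completers only. The risk is of a more favourable picture of first-time wear, with no comparator to offset it.

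The size cannot be determined from the documents. The illustration rests on an assumed 80% purchase intent, an assumed number of lens-related stoppers and an assumed 20- to 40-point gap. It runs from no effect with no stoppers to a fall in purchase intent of 7.3 percentage points with four (80.0 − 72.7) and 16.0 with ten (80.0 − 64.0). The plan does not provide for the data that would show where in this range the study lies.

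This should be fixed, though it does not invalidate an exploratory study whose results are clearly labelled as completer results.

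**What to change.** - Give the applicable CLDEQ-8, VAS and purchase items in REDCap at early exit, by link if the subject does not return. Give them also at Visit 2, so that a rating exists for those lost later. Items on a full week of wear or on the end of the study can be left out where they do not apply.
- Record the reason for stopping, with lens-related reasons separated from others such as scheduling.
- Report the numbers screened, dispensed lenses and completed.
- Report purchase intent over all subjects dispensed lenses, with lens-related stopping counted as a no, as a sensitivity figure beside the completer figure.
- Label Visit 3 scores as completer ratings. Show Visit 2 and exit scores separately and do not carry them forward, since early ratings from people still learning to wear lenses are not interchangeable with those at Visit 3.

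The cost is a few minutes per subject and a few lines of analysis, with no added subjects. Headline percentages may become less favourable. An exit survey is voluntary and will miss some people, so the disposition counts are needed in any case. The collection steps must be in place before the first subject leaves.
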